There is a critical need to understand which messages resonate among populations at-risk for specific diseases (e.g., CRC) and who may have concerns about engaging in early detection behaviors (e.g., CRCS) and may face disparities in exposure to (mis)information from online sources. Public health communicators have growing concerns about health misinformation on social media.²⁷ Evidence that misinformation spreads more widely and easily than accurate information online²⁸ suggests remedies may be needed to compete with such misinformation. For instance, researchers have used a text mining approach to identify misinformation about cancer screening on websites to assist health communicators to counter such messages publicly.²⁹ Other researchers found that gynecologic cancer misinformation appeared in about 30% of messages on the Chinese platform Weibo, with more misinformation presented about treatment than prevention.³⁰ That percentage mirrors work in the US on cancer information posted by parents on Facebook, where among posts including medical information, only 67% were accurate, with other posts being either inaccurate (19%) or conveying unproven treatments (14%).³¹ Research considering YouTube videos and respective page content about prostate cancer found that 77% of studied video included misinformation or biased content, and that there was a negative correlation between the scientific quality of a video and engagement (e.g., views and likes).³² Taken together, these descriptive studies suggest there is considerable misinformation present via social media, though none of the studies examined CRC or CRCS. Additionally, these descriptive studies provide insights into what information and misinformation exists in the public communication environment, but lack follow-up work to assess how people assess or intend to utilize this information in the future. So, while novel methods are being used to monitor the communication environment, the utility of these methods is falling short of making direct contributions to future communication efforts.

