Crowdsourcing formative evaluation research offers an outlet to identify strong message content, but there is limited evidence on its predictive validity in identifying messages that increase screening and sharing intentions. Extant research supports the use of crowds to assess content quality and generate new content, but there is still a need to establish predictive validity of the approach to determine that crowd selected messages are persuasive.³⁷ Establishing predictive validity of this approach requires consideration of how selected messages can affect key outcomes (e.g., CRCS intentions) and provide content that can be used for recommended communication strategies (e.g., targeting). Targeted delivery approaches have been successful promoting CRCS behaviors³⁸ and targeting by race has been effective in promoting cancer screening behaviors.³⁹ Message targeting by race involves tradeoffs for financially constrained campaigns, however, in that the strategy often requires more resources for message production and placement,⁴⁰ and few studies directly compare if race-targeted content outperforms messages found in pre-testing to appeal to a broad cross-section of the population. The most scientifically rigorous way to establish predictive validity of crowdsourced formative evaluation research and test content targeting by racial group preference is to conduct a randomized controlled trial (RCT). Selecting messages from the crowd rankings allows for categorization of

high-quality messages both overall and by racial group. This will allow us to design an RCT that provides direct evidence of predictive validity of the crowdsourcing approach for CRCS, and to determine if selecting targeted messages via crowdsourcing improve outcomes for primary (targeted) and secondary audience segments.

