Summary of study significance. Disparities in CRC diagnosis and outcomes, as well as suboptimal screening levels, may be due in part to limited knowledge and misinformation. Determining how the public health information environment contributes to reducing information disparities, and in turn screening disparities, offers an important opportunity to address this public health priority. Developing and validating a novel approach to monitoring and evaluating the public information environment using methodological innovations increasingly available to communication scientists. **The proposed project directly responds to the program announcement focus of utilizing and applying new cancer communication surveillance approaches to examine public health communication about CRC prevention and control.** Additionally, the project engages with a traditionally underserved population, Black Americans, who are at elevated risk of CRC.

B. INNOVATION

The present proposal's innovation is developing an overarching framework that functions to monitor and use the online information and message environment to facilitate efficient, timely, evidence-based communication recommendations for cancer control communication efforts. **Having a comprehensive framework to monitor, evaluate, generate, and disseminate accurate information that also demonstrates the ability to motivate action is a necessary next step to strategic cancer communication efforts.** The proposal accomplishes this by using a three-step process that (1) captures and analyzes digital and social media information and misinformation about CRCS, (2) uses a crowdsourcing approach to evaluate and generate information and messages found through monitoring efforts that are most appealing and effective with specific population segments at greater risk for CRC, and (3) tests if the messages identified as most appealing do indeed improve screening and message sharing intentions among target audiences. As such, this project will provide evidence on the efficacy of a conceptual framework to monitor and implement messages from the public information environment to improve cancer communication across the cancer continuum.

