Procedure and Message Integration. Once participants complete informed consent procedures, administered electronically by the survey contractor, the survey will begin. We will first present demographics questions followed by the wiki survey task, embedded within the larger survey platform. We will provide participants with instructions about how to complete the wiki survey component, as well as basic information about what the research study references when it mentions colon cancer screening. Based on procedures and our agreement with the contractor, participants will be told they can respond to as many message pairs that they like. The contractor estimates that participants will likely complete 20 to 25 choice pairs based on typical user engagement. After the first week of data collection, the PI ([name]) and one co-I ([name]) will oversee graduate students who will sift through crowd-generated messages to remove messages that duplicate information already in the message set, as well as messages that might be offensive or unrelated to the study. We will integrate valid, novel messages generated via crowdsourcing into the wiki survey on a weekly basis. The wiki survey will be programmed to prioritize presentation of the newly-added messages to even out how many times messages are evaluated—though presented messages will continue to be randomly presented in pairs to participants. This will occur every week for 10 weeks until data collection is complete for Study 2. With each pair of messages displayed, participants will be prompted with the following question: “Which of the two statements below is a better reason for you to have a colon cancer screening test?”

Measured Variables. The survey contractor will monitor and ensure data quality for participants within the AmeriSpeak/NORC panel and from the third-party provider. We will collect demographic information on participants including age, sex/gender identity, educational obtainment, ethnicity, income, employment status, housing type, access to health insurance, and CRCS status. Outside of demographic variables, the key outcomes for Study 2 will be the choices from the presented message pairs, as well as crowd-generated messages. We will use this information to rank the quality of messages but also provide information on how many messages researchers might expect to be generated by the crowd using this methodological approach, including considering how sex (as a biological variable) affects rankings.

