C.4 APPROACH: Specific Research Questions and Hypotheses

Study/Aim 2 – Wiki Survey

Wiki surveys offer a method for using the perceptions and perspectives of large groups of targeted audiences in evaluating and generating messages about a topic of interest. Still, less is known about how many unique messages researchers and practitioners are likely to generate using this approach. Related, there is scant evidence regarding the quality of messages generated by this approach to soliciting message ideas. Based on these unknowns about the utility of a crowdsourced approach to message generation via wiki surveys, we propose the following two research questions.

RQ: How many unique messages about CRCS are generated by wiki surveys in the context of CRCS?

C.6 APPROACH: Data Analysis Plan

Analyses for Study/Aim 2. The wiki survey approach of Study 2 requires analysis and aggregate ranking of people's message selections from message choice pairs. To analyze these data, we will fit a Bradley-Terry model. Engaging this approach allows us to generate a relative ranking of statements. More specifically, Bradley-Terry models use a generalized linear modeling approach to provide a log odds estimate regarding if one message will outperform another in a paired comparison with a one statement set as a reference item. Past work using wiki surveys has used the median item as the reference category,³⁷ which is the approach we will use for analyzing data from Study 2. The coefficients produced by the procedure can be used to rank messages where better performing messages have a higher value than lower performing messages. We will work with the statistical expert on the project to ensure the Bradley-Terry models fit for the Study 2 data, including fitting separate models to consider individual differences⁶² for factors such as education and access to insurance, and to account for non-independence of observations that arise from the fact that some respondents will choose to rate more argument pairs than other respondents.

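### Should the plan commit to checking the pooled message ranking by colorectal cancer screening (CRCS) status?

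*Combined protocol and SAP*

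**What the plan says.** C.3 (Procedure and Message Integration) puts one question with every pair: "Which of the two statements below is a better reason for you to have a colon cancer screening test". Recruitment in C.1 (Design overview) and C.3 (Participants) is by age, 45 to 74, and race, with 1,000 Black and 1,000 White adults. Screening history is neither an entry criterion nor a quota.

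Screening status appears once, at the end of the list of demographic items in C.3 (Measured Variables): "housing type, access to health insurance, and CRCS status". Its categories are not given there.

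C.6 fits a Bradley-Terry model to obtain a relative ranking of messages and adds separate models "for factors such as education and access to insurance". Its power paragraph speaks of a series of such models without listing them. Two other splits are mentioned: sex in C.3 ("including considering how sex (as a biological variable) affects rankings") and race in section A, where the crowd rankings are to identify "high-quality messages both overall and by racial group".

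C.2 says that the studies for all three aims will be registered on OSF.io. The questionnaire and that registration are not part of this document.

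**The concern.** The question asks for a reason that applies to the respondent personally. Someone with a recent colonoscopy and someone never screened may answer it from different positions, and the aggregate ranking combines them. Section A stresses people "who may have concerns about engaging in early detection behaviors", and section B describes a later step that "tests if the messages identified as most appealing do indeed improve screening and message sharing intentions among target audiences". Race, sex, education and insurance are each named for rankings or models. Screening status, arguably the variable closest to the question, is not.

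If most respondents were up to date and their preferences differed from those of the rest, the top of the pooled list could reflect people with the least to gain from the messages. A message that the unscreened disfavour could rank well, and none of the outputs named in the plan would show it. Two practical points add to the worry. A comparison chosen after the rankings are seen is weaker evidence than a planned one. And an item recording only whether someone was ever screened could not separate overdue from up-to-date respondents once the survey has closed.

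**Working it through.** **The plan's own figures.** 100 people × 2 groups × 10 weeks = 2,000 respondents. 2,000 × 15 pairs = 30,000 choices, as stated. 100 × 99 = 9,900 ordered pairs, as stated (4,950 unordered). Displays per message = 2 × 30,000 / 100 = 600 overall and 300 within each racial group, so the minimum of 300 in C.6 is met.

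**Assumptions.** The documents do not give the share u of respondents who are up to date. Section A gives only a 70.5% national goal, with actual rates below it. I take u = 0.4 to 0.7, 15 pairs each, 100 messages of similar strength and, at first, independent choices.

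**Precision by status.** The standard error (SE) of a message score against the average message is 2/√displays. Pooled: 2/√600 = 0.082. For the not-up-to-date group, choices = 30,000 × (1 − u) and displays = 600 × (1 − u):

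| u | Choices | Displays per message | SE |
|---|---|---|---|
| 0.4 | 18,000 | 360 | 0.105 |
| 0.5 | 15,000 | 300 | 0.115 |
| 0.6 | 12,000 | 240 | 0.129 |
| 0.7 | 9,000 | 180 | 0.149 |

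The contractor expects more, in that "participants will likely complete 20 to 25 choice pairs". That would give 240–480 displays at 20 pairs and 300–600 at 25.

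**When does the pooled ranking serve this group worse than its own?** Let preferences differ between the status groups by a standard deviation (SD) D across messages, in log-odds. As an estimate of the not-up-to-date scores, the pooled ranking has mean squared error SE_pooled² + u²D². The group's own ranking has SE_sub². They are equal at D = √(SE_sub² − SE_pooled²)/u.

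- u = 0.5: √(0.01333 − 0.00667)/0.5 = 0.163.
- u = 0.7: √(0.02222 − 0.00667)/0.7 = 0.178.
- Values at u = 0.4 and 0.6 lie between these (0.167).
- Within one racial group displays halve, so multiply by √2: 0.231–0.252.
- Repeated choices by one person are correlated. With an assumed design effect of 1.5, multiply by √1.5: 0.200–0.218 overall and 0.283–0.309 within race.

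Below these values pooling is the better estimator even for the group in question. A simulation of 300 runs at u = 0.5 and D = 0.163 gave root mean squared errors of 0.118 (own ranking) and 0.115 (pooled), which agrees with the formula.

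**What would a global test of message by status show?** It has 99 degrees of freedom and a 5% critical value of 123.2. Power = P(χ²₉₉ > 123.2/(1 + D²/SE_diff²)), with SE_diff = 0.163–0.178.

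| D | Independent choices | Design effect 1.5 |
|---|---|---|
| 0.10 | 0.63–0.74 | 0.40–0.49 |
| 0.15 | 0.98–0.995 | 0.87–0.93 |

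The test would find a difference large enough to favour the group's own ranking. A non-significant result would not show that the rankings agree.

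**Size of the reversal.** Suppose a pair stands at +0.5 log-odds in screened people and −0.5 in the 29.5% who are not (the complement of the 70.5% goal). The pooled probability is 0.705 × 0.622 + 0.295 × 0.378 = 0.550, or +0.20 log-odds, so the order does flip. But this assumes a between-group difference of 1.0 on one pair. The break-even D at u = 0.705 is 0.179, and 0.179 × √2 = 0.253 on the scale of a pair, so the example is about four times the break-even.

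**The case for a change.** The best argument for a change is timing. A line in C.6 and a well-worded status item cost little before launch. The item cannot be repaired afterwards, and a factor chosen late carries less weight. Status also has a more direct link to the question asked than education or insurance, which are named.

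Part of this stands: naming status, with its categories, would make the plan clearer. The rest goes too far for four reasons.

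- C.6 gives education and insurance as examples, so a model by status fits the plan as written. What would be lost is the comparison's pre-specified standing. The ability to make it would remain.
- A one-word entry in a list of variables does not show that the questionnaire item is undefined, and the OSF registration may settle both item and factor list.
- The question still has meaning for screened people. Section A describes tests that recur yearly, every five years or every ten, and C.3 frames the task as adherence to recommendations.
- The audiences that the document defines are Black and White adults aged 45 to 74. Section A's remark about concerns over early detection does not restrict them to people who are overdue, and whether selected messages work is left to the randomised study.

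**Conclusion.** The omission is real but is a matter of missing detail that analysts can fill sensibly from data already collected. Pooling is also a fair trade-off. Under the stated assumptions it estimates the not-up-to-date group's preferences as well as or better than a separate ranking until the difference between groups reaches an SD of about 0.16–0.18 log-odds, or 0.20–0.22 with a design effect of 1.5. The thresholds within race are higher still.

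These figures rest on an assumed up-to-date share and design effect, on 100 messages of similar strength, and on 15 choices per person. The documents give no evidence on whether preferences differ by status, so a larger difference cannot be ruled out. Equally, nothing shows that the pooled ranking is wrong or that message selection would change. Study 3's population and selection rule are not in this document. A descriptive ranking by status beside the pooled one, with its wider intervals stated, would be a reasonable optional report. The plan does not need amending for it.

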Design overview. For Study 2, we will contract a custom, crowdsourced wiki survey using a national sample of adults 45 to 74 years old—including 1000 individuals who self-identify as White or Caucasian and 1000 individuals who self-identify as Black or African American—to choose preferred messages curated from the social media monitoring occurring during the first year of Study 1. Data collection will occur over two and a half months, with 100 people from each targeted group participating every week. This approach allows us to integrate messages generated by participants, as well as new messages discovered during the continuing monitoring of social media messages. We will include 40 to 60 messages, to be displayed randomly in pairs, for the first week of data collection (see Figure 1). The original message set will be supplemented with crowd-generated messages on a weekly basis. Based on past wiki survey research,³⁷ we expect participants to generate approximately 800 message suggestions of which approximately 5% ($n = 40$) will be novel (i.e., not duplicates) to the message set. We expect each participant will respond to at least 15 randomized pairs of messages, totaling at least 30,000 message choices crowdsourced in the study.

C.2 APPROACH: Planning and Preparation, IRB

We will develop study protocols that protect human subjects in accordance with a single-site IRB (at Iowa State University), in collaboration with IRBs at collaborating institutions, as required by federal regulations and university operating policies. Research related to Aim 1 does not require IRB approval because it does not involve human participants. Studies for all three aims will be registered with OSF.io, the registration website of The Open Science Framework, and we will also register the RCT (Aim 3) on clinicaltrials.gov. The PI will work with the survey company (AmeriSpeak/NORC) to program and implement the studies to be carried out for Aims/Studies 2 and 3 to ensure that they protect the health, safety and rights of human subjects.

[figure not shown]

Figure 1. Sample Choice Screen from Wiki Survey

C.3 APPROACH: Aim 2, Crowdsourcing Message Evaluation and Generation Using Wiki Surveys

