Message Selection. The grant team will seed the initial list of choices with at least 40 to 60 messages selected from Study 1. Messages will be selected from the library collected during Study 1 from social media platforms and popular health websites. All messages presented to participants will be reviewed by the medical consultant on the grant ([name]) to ensure participants are not rating messages that include any misleading or incomplete information. Messages will be selected by the grant team based on their review of the library of message and suggestions from the medical consultant who has research and practice experience with cancer screening and health disparities. Once the messages are selected, we will work with our contracted survey provider—AmeriSpeak/NORC—to input the messages into the customized wiki survey tool.

Participants. AmeriSpeak/NORC will provide a sample that combines members of their panel and a third-party non-probability panel for a portion of the sample of Black Americans. This is necessary given the goal of having a large sample of a traditional under researched (in communication science) and underserved population (Black Americans between the ages of 45 and 74). For Study 2, the total recruited sample ($N = 2,000$) will be evenly split between White American adults aged 45 to 74 ($n = 1,000$) and Black American adults aged 45 to 74 ($n = 1,000$). The reason for sampling participants from age 45 is that many screening recommendation options for higher risk populations—including Black Americans and individuals with other comorbidities—begin at age 45. *Individuals who participate in Study 2 will not be eligible for Study 3.* We estimate Study 2 will take participants approximately 15 to 20 minutes to complete.

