Power analysis. Study/Aim 2 will fit a series of Bradley-Terry models to the choice data provided by the wiki survey and this analytical approach produces ranking that can be produced with varied sample sizes. Given the potential to test up to 100 messages by adding crowd-generated messages, the study design will display each message at least 300 times and all possible choice combinations ($n = 9,900$ assuming 100 message options) will be evaluated at least once, which is recommended in paired comparison data.⁶⁴

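### Messages are ranked on Bradley-Terry point estimates with no stated precision, so rankings by racial group could differ through noise alone

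*Combined protocol and SAP*

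**What the plan says.** The combined protocol and SAP, section C.6 (Data Analysis Plan, Study/Aim 2), fits a Bradley-Terry model with the median item as reference and reads the order from the estimates: "The coefficients produced by the procedure can be used to rank messages where better performing messages have a higher value than lower performing messages". It foresees separate models for factors such as education and insurance, and promises to allow for respondents who rate more pairs than others, without naming a method. It states no standard error, interval or treatment of messages that cannot be told apart.

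The Power analysis paragraph that follows says that "this analytical approach produces ranking that can be produced with varied sample sizes". It adds a floor of 300 displays per message and the coverage of all 9,900 combinations of 100 messages.

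The use of the ranking is described in section A (Significance): "Selecting messages from the crowd rankings allows for categorization of" high-quality messages, overall and for each racial group, as input to the later randomised trial. No list size or selection rule is given.

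**The concern.** Any set of paired choices yields an order, even choices made at random. That a ranking can be produced therefore says nothing about whether it is right. Display counts and pair coverage describe how often messages are seen. They become a justification of sample size only when turned into a standard error, and the plan does not do this.

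The issue bears most on the rankings by race. Each uses half the choices, and the two lists are meant to be set side by side to find targeted content. If both are cut on point estimates, sampling error alone will make them differ, and the difference can be taken for a difference in preference.

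**Working it through.** **Inputs from the plan.** 2,000 participants, 1,000 per racial group (C.3, Participants). Each answers "at least 15 randomized pairs of messages, totaling at least 30,000 message choices crowdsourced in the study" (C.1, Design overview). Number of messages: "Given the potential to test up to 100 messages by adding crowd-generated messages" (Power analysis). The starting set is 40 to 60 and about 40 novel messages are expected (C.1), so 80 to 100 in all.

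**The plan's own figures.** 2,000 × 15 = 30,000 choices. 100 × 99 = 9,900 ordered pairs. Both reproduce. Average displays per message are 2 × 30,000 / 100 = 600. Within one racial group, 1,000 × 15 = 15,000 choices give 2 × 15,000 / 100 = 300.

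**Precision, with no assumption about spread.** For messages of similar strength each comparison carries information of about 1/4, so SE ≈ 2/√n for n displays. The difference separable at 95% is 1.96 × √2 × SE.

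| Choices (100 messages) | Displays | SE (log-odds) | Separable difference | Win rate |
|---|---|---|---|---|
| 30,000, pooled | 600 | 2/√600 = 0.082 | 0.226 | 55.6% |
| 15,000, one group | 300 | 2/√300 = 0.115 | 0.320 | 57.9% |

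A message that only just meets the plan's floor of 300 displays has the second row's SE even in the pooled ranking. The 0.32 also applies, approximately, to one message compared between the two groups, since that too is a difference of two estimates with SE 0.115. All of this precedes any allowance for repeated choices by a respondent.

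**Effect on a selected list.** This needs the true spread of message strength, which the plan does not give. It is assumed here and varied. The top ten is illustrative. Method: random pairs, independent choices, normally distributed true strengths, Bradley-Terry maximum likelihood, 200 simulated studies per row, 100 messages.

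| Assumed SD (log-odds) | Wrong in top ten, 30,000 choices | Wrong in top ten, 15,000 choices | Neighbours reversed, 30,000 choices |
|---|---|---|---|
| 0.1 | 4.8 | 5.7 | 48% |
| 0.2 | 2.7 | 3.7 | 47% |
| 0.3 | 2.1 | 2.7 | 45% |
| 0.5 | 1.4 | 1.7 | 43% |
| 1.0 | 0.8 | 1.1 | 39% |

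**Two groups with the same preferences.** Two independent samples of 15,000 choices drawn from the same true strengths share on average only about 5.0 (SD 0.2) to 7.5 (SD 0.5) of their top tens.

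**Dependence within respondents.** Adding respondent-level variation in preferences (SD 1.0) at 30,000 choices raises the wrong entries from 1.4 to 1.7 at message SD 0.5, so the independent-choice figures are somewhat optimistic.

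**The case against.** Several points on the other side are sound.

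- *The simulated sizes rest on an assumed spread, on 100 messages and on a list of ten.* This stands. At SD 1.0 the pooled list has 0.8 wrong entries, and with 60 messages and SD 0.5 it has 0.9. At the 80 messages the plan's own counts also allow, the figures are 2.45, 1.73 and 1.18 at SD 0.2, 0.3 and 0.5. The standard errors need no spread.
- *30,000 is a floor.* "The contractor estimates that participants will likely complete 20 to 25 choice pairs based on typical user engagement", which makes 40,000 to 50,000 choices. At 50,000 the SE is 2/√1,000 = 0.063 pooled and 2/√500 = 0.089 per group, with separable differences of 0.18 and 0.25. That is better, but still not stated in the plan.
- *The pooled list is nearly as good as the true one.* This stands. At SD 0.2 to 0.5 the rank correlation with the true order is 0.91 to 0.98. The mean strength of the chosen ten falls short of the true ten by 0.026 to 0.011 log-odds, under 0.7 percentage points of win rate (0.026 / 4 = 0.0065).
- *C.6 makes no claim of significance between messages and does not itself define high quality.* Correct. The selection is announced in section A.
- *Non-independence and a statistical expert are mentioned in C.6.* True, but no method is given and nothing links it to uncertainty in ranks.

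A reader might infer from the reversal column that the ranking is close to useless. It is not: among 100 messages neighbours are almost tied, and most reversals are trivial. A reader might also infer that the pooled ranking would send clearly inferior messages to the trial, so that a null trial result could be put down to ranking noise. The small loss in mean strength does not support that.

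**Conclusion.** The concern holds in a limited form. The plan orders messages by point estimates, states no precision, and offers exposure counts under the heading of power. With 100 messages the delivered SE is about 0.08 log-odds pooled and 0.115 per racial group.

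For an assumed SD of 0.2 to 0.5, about 1 to 3 of an illustrative top ten are wrong overall, at little cost. The more serious consequence is in the lists by race: about 2 to 4 of ten wrong in each, and an overlap of only about 5 to 7.5 between groups that do not differ at all. As the plan stands, such lists could be reported as race-specific with no check against chance. The problem shrinks with a wider spread, fewer messages or more choices, and grows with a narrower spread. The documents do not say which applies.

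**What to change.** 1. In the Power analysis paragraph, replace the sentence on varied sample sizes with the precision delivered: for 100 messages, SE about 0.08 and separable difference about 0.23 log-odds at 30,000 choices; about 0.115 and 0.32 at 15,000 choices in one racial group. Say that repeated choices by a respondent are not yet allowed for.
2. In C.6, name racial group among the separate models. Refit the model in bootstrap samples that resample respondents, overall and within each racial group. Report 95% intervals for coefficients and ranks, and each message's probability of being in the selected set. Resampling respondents also supplies the missing method for non-independence.
3. State that one message is said to outperform another, or to rank differently by race, only when the interval for that difference excludes zero. For the comparison by race, centre the coefficients in the same way in both groups.

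A tier rule or a probability cut-off for high-quality messages is optional.

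The cost is SAP wording and a few hundred refits of a model with about 100 parameters. No new data are needed. The downside is fewer firm statements about exact order.

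### Does blaming non-independence on unequal numbers of ratings, instead of on repeated choices by one respondent, undermine the Aim 2 ranking analysis?

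*Combined protocol and SAP*

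**What the plan says.** Section C.6 (Analyses for Study/Aim 2) fits a Bradley-Terry model to the paired choices and ranks messages by their coefficients, with the median item as reference. With the project's statistical expert, the team will also account for "non-independence of observations that arise from the fact that some respondents will choose to rate more argument pairs than other respondents". No variance method is named, and the respondent is not named as the cluster.

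Two places show that every respondent contributes repeated choices. The Design overview in section C.1 states: "We expect each participant will respond to at least 15 randomized pairs of messages, totaling at least 30,000 message choices crowdsourced in the study". Section C.3 (Procedure and Message Integration) sets no upper limit, since "participants will be told they can respond to as many message pairs that they like", and adds: "The contractor estimates that participants will likely complete 20 to 25 choice pairs based on typical user engagement".

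Rankings are to be looked at by group in three places. C.3 (Measured Variables) ends with "including considering how sex (as a biological variable) affects rankings". C.6 mentions "fitting separate models to consider individual differences", with education and insurance as examples. Section A speaks of using the crowd rankings to identify "high-quality messages both overall and by racial group". None of these comes with a hypothesis test, significance level or interval.

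**The concern.** The clause appears to name the wrong cause. If everyone rated exactly 15 pairs there would be no unequal counts, and on a literal reading nothing to correct. Yet the 15 choices of one person would still share that person's preferences and be correlated. Conversely, if counts differed widely but respondents had no preferences of their own, the choices would be independent.

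An analyst who followed the wording to the letter might reweight heavy raters and then treat the choices as independent. That would deal with influence and leave the within-respondent correlation in place. Standard errors would be too small, and a formal comparison of rankings between men and women, or between White and Black respondents, would find differences too often.

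**Working it through.** **Reproducing the plan's figure.** Inputs: 2,000 respondents (C.3, Participants) and at least 15 pairs each (C.1). 2,000 × 15 = 30,000 choices, as stated. Each block of about 15 choices therefore comes from one person.

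**Where the dependence comes from.** The generic design effect is 1 + ((1 + cv²)·m − 1)·ICC, with m the mean number of choices per respondent and cv the coefficient of variation of the counts. The ICC is not in the documents; 0.05 is used for illustration.
- Equal counts, m = 15, cv = 0: 1 + 14 × 0.05 = 1.70.
- Unequal counts, m = 15, cv = 1: 1 + (2 × 15 − 1) × 0.05 = 2.45.
- One choice each (m = 1, cv = 0), any ICC: 1.00.
- ICC = 0, any spread of counts: 1.00.

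Repeated choices are thus the source and unequal counts the amplifier. The technical point is correct.

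**How much of this reaches the message coefficients.** Far less than the generic formula suggests, because a respondent seldom meets the same message twice. The mean number of exposures per message is 2m/J for J messages: 2 × 15/100 = 0.3 at the low end and 2 × 25/40 = 1.25 at the high end.

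Bradley-Terry data were simulated with 2,000 respondents and 40, 60 or 100 messages (25 replicates per setting, pairs drawn uniformly). The table gives the respondent-clustered variance divided by the naive variance. The preference SD (logits) and the spread of counts are assumptions.

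| Pairs per respondent | SD 0 | SD 0.5 to 1 | SD 2 |
|---|---|---|---|
| 1 each | 1.00 | 1.00 | 1.00 |
| 15 each | 1.00 | 1.01–1.09 | 1.05–1.17 |
| 22 each | 1.00 | 1.02–1.14 | 1.09–1.25 |
| minimum 15, mean 22 | 1.00 | 1.02–1.15 | 1.09–1.28 |
| 10% rate 85, the rest 15 | 1.00 | 1.04–1.27 | 1.15–1.48 |

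Even the most extreme cell means a standard error too small by a factor of √1.48 ≈ 1.22. A separate simulation, with preferences shared over 5 message themes, 50 to 100 messages and SD 0.5 to 1.0, gave ratios of 1.011 to 1.107. The shortfall in the standard error is then 1 − 1/√1.011 ≈ 0.5% to 1 − 1/√1.107 ≈ 5%.

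**What it would do to a formal comparison.** The plan has no such test, so one was constructed: a 5% likelihood-ratio test that two groups of 1,000 share one ranking, with choices treated as independent, no true difference and 5 themes. At exactly 15 pairs each (1,500 runs, simulation error about 0.6 to 0.8 points) it rejected as follows.

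| Messages | SD 0 | SD 0.5 | SD 1.0 |
|---|---|---|---|
| 100 | 5.1% | 5.9% | 8.5% |
| 50 | 5.9% | 7.1% | 9.9% |

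The excess over the SD 0 control is 0.8 and 1.2 points at SD 0.5, and 3.4 and 4.0 points at SD 1.0. The highest rate in any setting, 14.8%, needed SD 1.0 together with strongly unequal counts (floor 15, mean 22, log-SD 1.0), which is the feature the plan does name.

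**What it does to the ranking.** Cluster-robust variance or a respondent-level bootstrap leaves the coefficients, and so the order of the messages, unchanged.

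**The case for a change.** The strongest case for a change is that this clause is the plan's only instruction on dependence, so its wording may decide what is done. It points towards adjusting counts, and the excess rejection at exactly 15 pairs each cannot be removed by any such adjustment. Group comparisons are promised, and judging whether two rankings really differ needs valid uncertainty. One corrected sentence would cost nothing in data or sample size.

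Two parts of this stand: the clause is incomplete, and any later interval or test should treat the respondent as the unit. The rest is weaker. The sentence's main promise is to account for non-independence, and it already locates the problem in respondents who rate several pairs. An analyst who then treated those choices as independent would break that promise. Unequal counts are also a proper concern for a ranking: with unlimited rating, heavy raters can move the order itself if their preferences differ from the rest, whereas within-respondent correlation chiefly affects standard errors. Finally, the group comparisons as written are descriptive. Fitting models separately gives separate rankings, and taking the top messages in each group needs no test between groups.

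One limit applies to the calculations. They assume uniformly random pairs, while C.3 gives priority to newly added messages. That raises repeat exposure to those messages and could raise the inflation for them; the amount was not estimated.

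**Conclusion.** No change to the plan is needed. The explanatory clause in C.6 is imprecise, but the commitment it belongs to is the right one, and a statistician carrying it out would sensibly cluster by respondent. The 30,000 choices, the ranking by coefficients and the research question on the number of unique messages are all unaffected. The wording would matter only if intervals or tests were later used to compare rankings between groups, which the documents do not specify. Even then the likely effect is small: single-message standard errors about 0.5% to 5% too small, and about 1 to 4 points of excess rejection at 15 pairs each. These sizes rest on assumed preference SDs of 0.5 to 1.0, 5 themes and uniform pairing, none of which the documents give. The 14.8% rejection rate belongs to a constructed test under the least favourable assumptions tried and should not be read as a consequence of this plan.
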